1. INTRODUCTION

This statistical analysis plan (SAP) specifies definitions of analysis sets, key derived variables, and the statistical analysis methods for the planned analyses of safety, reactogenicity, and immunogenicity data for the planned primary and final analysis of the study. The primary and final analysis will be performed on unblinded data. The current SAP is based on Clinical Trial Protocol amendment 7 of VAC31518COV3003. Titles, mock-ups, and programming instructions for all statistical outputs (tables, figures and listings) will be provided in a separate document titled Data Presentation Specifications (DPS). This SAP is to be finalized prior to final database lock.

1.1. Objectives and Endpoints for Participants in the Main Study

Objectives	Endpoints
Primary	

To demonstrate non-inferiority (NI) in the following sequential order:
 
 NI after 1-dose of Ad26.COV2.S 9×10^{10} vp vs 1-dose of Ad26.COV2.S 5×10^{10} vp (release titer) NI after 1 dose of Ad26.COV2.S 2.5×10^{10} vp vs 1-dose of Ad26.COV2.S 5×10^{10} vp (release titer) NI after 1 dose of Ad26.COV2.S 7×10^{10} vp vs 1-dose of Ad26.COV2.S 5×10^{10} vp (release titer) NI after 1 dose of Ad26.COV2.S 3.5×10^{10} vp vs 1-dose of Ad26.COV2.S 5×10^{10} vp (release titer) NI after 1-dose of Ad26.COV2.S 1.25×10^{10} vp vs 1-dose of Ad26.COV2.S 5×10^{10} vp (release titer) 	
 Binding antibody concentrations to SARS-CoV-2 S protein as measured by ELISA 28 days after first vaccination NI will be demonstrated in terms of humoral immune response expressed by the GMCs of S-ELISA, 28 days post-dose 1, using a NI margin of 2/3 for the GMC ratio (GMC 9×10^{10} vp, 2.5×10^{10} vp, 7×10^{10} vp, 3.5×10^{10} vp, or 1.25×10^{10} vp/GMC 5×10^{10} vp)

To demonstrate NI in the following sequential order:
 
 NI after 2-doses of Ad26.COV2.S 9×10^{10} vp vs 1 dose of Ad26.COV2.S 5×10^{10} vp (release titer) NI after 2-doses of Ad26.COV2.S 9×10^{10} vp vs 2-doses of Ad26.COV2.S 5×10^{10} vp (release titer) 	
 Binding antibody concentrations to SARS-CoV-2 S protein as measured by ELISA 14 days after vaccination 2 NI will be demonstrated in terms of humoral immune response expressed by the GMCs of S-ELISA, 14 days post-dose 2 (9×10^{10} vp, 2.5×10^{10} vp, 7×10^{10} vp, 3.5×10^{10} vp, or 1.25×10^{10} vp) and 28 days post-dose 1 or 2 (5×10^{10} vp), using a NI margin of 2/3 for the GMC ratio (GMC [9×10^{10} vp, 2.5×10^{10}, 7×10^{10} vp, 3.5×10^{10} vp, or 1.25×10^{10} vp]/GMC 5×10^{10} vp)

Objectives	Endpoints

 NI after 2-doses of Ad26.COVID-19 2.5×10^{10} vp vs 1 dose of Ad26.COVID-19 5×10^{10} vp (release titer) NI after 2-doses of Ad26.COVID-19 2.5×10^{10} vp vs 2-doses of Ad26.COVID-19 5×10^{10} vp (release titer) NI after 2-doses of Ad26.COVID-19 7×10^{10} vp vs 1 dose of Ad26.COVID-19 5×10^{10} vp (release titer) NI after 2-doses of Ad26.COVID-19 7×10^{10} vp vs 2-doses of Ad26.COVID-19 5×10^{10} vp (release titer) NI after 2-doses of Ad26.COVID-19 3.5×10^{10} vp vs 1 dose of Ad26.COVID-19 5×10^{10} vp (release titer) NI after 2-doses of Ad26.COVID-19 3.5×10^{10} vp vs 2-doses of Ad26.COVID-19 5×10^{10} vp (release titer) NI after 2-doses of Ad26.COVID-19 2.5×10^{10} vp vs 1 dose of Ad26.COVID-19 5×10^{10} vp (release titer) NI after 2-doses of Ad26.COVID-19 2.5×10^{10} vp vs 2-doses of Ad26.COVID-19 5×10^{10} vp (release titer) NI after 2-doses of Ad26.COVID-19 1.25×10^{10} vp vs 1-dose of Ad26.COVID-19 5×10^{10} vp (release titer) NI after 2-doses of Ad26.COVID-19 1.25×10^{10} vp vs 2-doses of Ad26.COVID-19 5×10^{10} vp (release titer) 	
Secondary To assess the humoral immune response and durability to Ad26.COVID-19 across all groups, at all immunogenicity blood collection timepoints.	
 Serological response to vaccination and binding antibody GMCs to SARS-CoV-2 S protein as measured by ELISA, or equivalent assay

Objectives	Endpoints
To assess the safety and reactogenicity of Ad26.COVID-19 administered at several dose levels.	
 Solicited local and systemic AEs for 7 days after each vaccination Unsolicited AEs for 28 days after each vaccination SAEs throughout the study (from first vaccination until end of the study) Adverse events of special interest (AESIs [from first vaccination until end of the study]) MAAEs (until 6 months post-dose 2) AEs leading to study discontinuation (during the entire study) for all participants following vaccination
Exploratory To further explore humoral immune responses to Ad26.COVID-19 across all groups at all or selected blood collection timepoints.	Exploratory analyses may include the following: 
 SARS-CoV-2 neutralization as assessed by SARS-CoV-2 neutralization assays VNA (wtVNA and/or psVNA) including neutralization of emerging SARS-CoV-2 SARS-CoV-2 binding antibodies against emerging SARS-CoV-2 variants as assessed by S-ELISA or equivalent assay Adenovirus neutralization Functional and molecular antibody characterization including Fc-mediated viral clearance, avidity, Fc characteristics, immunoglobulin (Ig) subclass and IgG isotype Analysis of circulating Spike protein Epitope-specificity characterization of antibodies Cytokine profiling: Analysis of cytokines, chemokines, and other proteins of the innate or adaptive immune response in the serum or plasma Passive transfer: Analysis of immune mediators correlating with protection

Objectives	Endpoints
	against experimental SARS-CoV-2 challenge in a suitable animal model
To assess the correlation between the binding antibody (ELISA) titers and neutralizing antibody (VNA) titers to SARS-CoV-2, in a subset of participants at selected timepoints.	
 Correlation between ELISA (SELISA; EU/mL) and VNA (wild-type virus [wt]VNA and/or pseudovirion [ps]VNA) titers at selected timepoints
To assess for the occurrence of asymptomatic SARS-CoV-2 infection.	
 The number of participants with positive non-S protein ELISA (eg, nucleocapsid [N] protein ELISA).
To examine the immune response in vaccinated individuals with prior or breakthrough infection	
 SARS-CoV-2 neutralizing titers in serum measured by a VNA (wild-type virus and/or pseudovirion expressing S protein) SARS-CoV-2-binding antibodies measured by ELISA: Analysis of antibodies binding to the SARS-CoV-2 S protein
To assess hematology laboratory parameters before and after Ad26.COVID2.S administration.	
 Including but not limited to: Lupus anticoagulants, anti-β2 glycoprotein, anti-cardiolipin, D-dimers, and anti-PF4

GMC=geometric mean concentration

1.2. Objectives and Endpoints for Participants in the Sub Study

Objectives	Endpoints
Secondary	
To assess the humoral immune response and durability to Ad26.COVID2.S across all groups in the sub study, at all blood collection timepoints.	
 Serological response to vaccination and binding antibody GMCs to SARS.COVID-2 S protein as measured by ELISA, or equivalent assay.
To assess the safety and reactogenicity of Ad26.COVID2.S administered at several dose levels	
 Solicited local and systemic AEs for 7 days after each vaccination Unsolicited AEs for 28 days after each vaccination SAEs throughout the study (from first vaccination until end of the study) Adverse events of special interest (AESIs [from first vaccination until end of the study]) MAAEs (until 6 months post-dose 2)

Exploratory	
To further explore humoral immune response to Ad26.COVID-19 across all groups in the sub study at all or selected blood collection timepoints.	
Exploratory analyses may include the following:
 
 • SARS-CoV-2 neutralization as assessed by SARS-CoV-2 neutralization assays VNA (wtVNA and/or psVNA) including neutralization of emerging SARS-CoV-2 variants • SARS-CoV-2 binding antibodies against emerging SARS-CoV-2 variants as assessed by S-ELISA or equivalent assay • Adenovirus neutralization • Functional and molecular antibody characterization including Fc-mediated viral clearance, avidity, Fc characteristics, immunoglobulin (Ig) subclass and IgG isotype • Analysis of circulating Spike protein • Epitope-specificity characterization of antibodies • Cytokine profiling: Analysis of cytokines, chemokines, and other proteins of the innate or adaptive immune response in the serum or plasma
To assess the correlation between the binding antibodies (ELISA) titers and neutralizing antibody (VNA) titers to SARS-CoV-2, in a subset of participants at selected timepoints.	Correlation between ELISA (S-ELISA; EU/mL) and VNA (wild-type virus [wt]VNA and/or pseudo virion [ps]VNA) titers at selected timepoints
To assess for the occurrence of asymptomatic SARS-CoV-2 infection.	The number of participants with positive non-S protein ELISA or equivalent assay (e.g., nucleocapsid [N] protein ELISA).
To examine the immune response in vaccinated individuals with prior or breakthrough infection	
SARS-CoV-2 neutralizing titers in serum measured by a VNA (wild-type virus and/or pseudo virion expressing S protein)
 
SARS-CoV-2 binding antibodies measured by ELISA: Analysis of antibodies binding to the SARS-CoV-2 S protein

To evaluate the innate, pro-inflammatory and other potentially relevant responses to	Analysis of messenger ribonucleic acid (mRNA) expression levels of vaccine-induced

Ad26.COVID2.S vaccination at selected timepoints.	innate responses including inflammatory and coagulation-related mediators. Analysis of cytokines, chemokines, and other proteins- or lipids mediators of the innate immune response.
To assess hematology laboratory parameters before and after Ad26.COVID2. S administration.	Include but not limited to: Lupus anti-coagulants, anti- β 2 glycoprotein, ant-cardiolipin, D-dimers, and anti-PF4

Ad26= adenovirus 26: GMC= geometric mean concentration

If a correlate or threshold for protection against COVID-19 is established in terms of humoral immunity, then a statistical comparison to that correlate or threshold will substitute non-inferiority testing to immune responses to vaccine at release, as outlined in a revised analytical plan.

1.3. Study Design

Main Study

This is a randomized, double-blind Phase 3 study to evaluate 6 dose levels of Ad26.COVID2.S administered as a 2-dose schedule in healthy adults. In this main study, the safety, reactogenicity, and immunogenicity of 1 dose (dose 1 of the 2-dose regimen) and 2-doses of Ad26.COVID2.S will be evaluated. The lower dose (3.5×10^{10} vp, 2.5×10^{10} vp, and 1.25×10^{10} vp) levels mimic vaccine degradation to enable determination of product expiry. In order to increase the end of shelf-life specifications a potential target release titer of 7×10^{10} vp will be evaluated. A higher titer of 9×10^{10} vp will also be evaluated as is the upper limit of the release range (potential maximum vp at release). The study population will consist of healthy men and women aged between 18 and 55 years (inclusive), who have not previously received a vaccine against COVID-19 and have not had prior exposure to SARS-CoV-2 as assessed by local serology testing. Participants will receive Ad26.COVID2.S administered IM.

The study duration from screening until the last follow-up visit will be at least 8 months per participant. The study will consist of a 28-day screening phase with vaccinations on Day 1 and Day 57, and a follow-up of at least 6 months after the last vaccination.

A target of approximately, 1,350 participants (225 participants per active vaccine group) in the main study will be randomized in parallel in a 1:1:1:1:1:1 ratio to 1 of 6 vaccination groups in this study. Participants will receive a 2-dose vaccination regimen at different dose levels (9×10^{10} vp, 2.5×10^{10} vp, 7×10^{10} vp, 5×10^{10} vp, 3.5×10^{10} vp, and 1.25×10^{10} vp).

Table 2: Schematic Overview of Main Study Design and Groups

Group	N	Day 1 Vaccination 1	Day 57 Vaccination 2
1	For NI ~ 225	Ad26.COV2.S 9×10^{10} vp	Ad26.COV2.S 9×10^{10} vp
2	For NI ~ 225	Ad26.COV2.S 7×10^{10} vp	Ad26.COV2.S 7×10^{10} vp
3	For NI ~ 225	Ad26.COV2.S 5×10^{10} vp	Ad26.COV2.S 5×10^{10} vp
4	For NI ~ 225	Ad26.COV2.S 3.5×10^{10} vp	Ad26.COV2.S 3.5×10^{10} vp
5	For NI ~ 225	Ad26.COV2.S 2.5×10^{10} vp	Ad26.COV2.S 2.5×10^{10} vp
6	For NI ~ 225	Ad26.COV2.S 1.25×10^{10} vp	Ad26.COV2.S 1.25×10^{10} vp

Sub Study

Per amendment 5, an additional enrollment of adult participants 18 to 55 years, inclusive, will enroll into the sub study, into group 1, 3, 5 and 6 to further characterize the innate, pro-inflammatory and other relevant (e.g., pro-thrombotic) response to the Ad26.COV2.S to better understand a possible risk to TTS events. Participants will receive Ad26.COV2.S administered IM.

A target of approximately 240 participants (approximately 40 seronegative and approximately 20 seropositive participants per dose regimen) will be enrolled in the sub study and will receive a 2-dose vaccination regimen at either 9×10^{10} vp, 5×10^{10} vp, 2.5×10^{10} vp or 1.25×10^{10} vp.

Table 3 : Schematic Overview of Study Design and Groups for the Sub Study

Group	N seronegative	N seropositive	Day 1 Vaccination 1	Day 57 Vaccination 2
1	N ~ 40	N ~ 20	Ad26.COV2.S 9×10^{10} vp	Ad26.COV2.S 9×10^{10} vp
3	N ~ 40	N ~ 20	Ad26.COV2.S 5×10^{10} vp	Ad26.COV2.S 5×10^{10} vp
5	N ~ 40	N ~ 20	Ad26.COV2.S 2.5×10^{10} vp	Ad26.COV2.S 2.5×10^{10} vp
6	N ~ 40	N ~ 20	Ad26.COV2.S 1.25×10^{10} vp	Ad26.COV2.S 1.25×10^{10} vp

2. STATISTICAL HYPOTHESES

The primary objective of this study is to demonstrate the NI, in terms of humoral immune response, of 1-dose and 2-doses of 9×10^{10} vp, 2.5×10^{10} vp, 7×10^{10} vp, 3.5×10^{10} vp, and 1.25×10^{10} vp Ad26.COV2.S versus 1-dose and 2-doses of 5×10^{10} vp Ad26.COV2.S (release titer).

Formal NI testing will be applied to demonstrate NI of 1-dose and 2-doses of 9×10^{10} vp, 2.5×10^{10} vp, 7×10^{10} vp, 3.5×10^{10} vp and 1.25×10^{10} vp Ad26.COV2.S versus 1-dose and 2-doses of 5×10^{10} vp Ad26.COV2.S (release titer), using a NI margin of 2/3 for the GMC ratios.

The following 2 sets of hypotheses (1 dose and 2 doses) will independently be tested sequentially:

Post-dose 1

- 1a) NI after 1-dose of Ad26.COVID-19 9×10^{10} vp versus 1-dose of Ad26.COVID-19 5×10^{10} vp (release titer)
- 1b) NI after 1-dose of Ad26.COVID-19 2.5×10^{10} vp versus 1-dose of Ad26.COVID-19 5×10^{10} vp (release titer)
- 1c) NI after 1-dose of Ad26.COVID-19 7×10^{10} vp versus 1-dose of Ad26.COVID-19 5×10^{10} vp (release titer)
- 1d) NI after 1-dose of Ad26.COVID-19 3.5×10^{10} vp versus 1-dose of Ad26.COVID-19 5×10^{10} vp (release titer)
- 1e) NI after 1-dose of Ad26.COVID-19 1.25×10^{10} vp versus 1-dose of Ad26.COVID-19 5×10^{10} vp (release titer)

In this set, NI will be demonstrated in terms of humoral immune response expressed by the GMCs of S-ELISA, 28 days post-dose 1, using a NI margin of 2/3 for the GMC ratio (GMC [9×10^{10} vp, 2.5×10^{10} vp, 7×10^{10} vp, 3.5×10^{10} vp, or 1.25×10^{10} vp]/GMC 5×10^{10} vp).

Post-dose 2

[figure not shown]
- 2a1) NI after 2-doses of Ad26.COVID-19 9×10^{10} vp versus 1-dose of Ad26.COVID-19 5×10^{10} vp (release titer)
- 2a2) NI after 2-doses of Ad26.COVID-19 9×10^{10} vp versus 2-doses of Ad26.COVID-19 5×10^{10} vp (release titer)
- 2b1) NI after 2-doses of Ad26.COVID-19 2.5×10^{10} vp versus 1-dose of Ad26.COVID-19 5×10^{10} vp (release titer)
- 2b2) NI after 2-doses of Ad26.COVID-19 2.5×10^{10} vp versus 2-doses of Ad26.COVID-19 5×10^{10} vp (release titer)
- 2c1) NI after 2-doses of Ad26.COVID-19 7×10^{10} vp versus 1-dose of Ad26.COVID-19 5×10^{10} vp (release titer)
- 2c2) NI after 2-doses of Ad26.COVID-19 7×10^{10} vp versus 2-doses of Ad26.COVID-19 5×10^{10} vp (release titer)
- 2d1) NI after 2-doses of Ad26.COVID-19 3.5×10^{10} vp versus 1-dose of Ad26.COVID-19 5×10^{10} vp (release titer)
- 2d2) NI after 2-doses of Ad26.COVID-19 3.5×10^{10} vp versus 2-doses of Ad26.COVID-19 5×10^{10} vp (release titer)

2e1) NI after 2-doses of Ad26.COV2.S 1.25×10^{10} vp versus 1-dose of Ad26.COV2.S 5×10^{10} vp (release titer)

2e2) NI after 2-doses of Ad26.COV2.S 1.25×10^{10} vp versus 2-doses of Ad26.COV2.S 5×10^{10} vp (release titer)

In this set, NI will be demonstrated in terms of humoral immune response expressed by the GMCs of S-ELISA, 14 days post-dose 2 (9×10^{10} vp, 2.5×10^{10} vp, 7×10^{10} vp, 3.5×10^{10} vp, or 1.25×10^{10} vp) and 28 days post-dose 1 or 14 days post-dose 2 (5×10^{10} vp), using a NI margin of 2/3 for the GMC ratio (GMC [9×10^{10} vp, 2.5×10^{10} vp, 7×10^{10} vp, 3.5×10^{10} vp, or 1.25×10^{10} vp])/GMC 5×10^{10} vp below depicts a tree-based schema for testing the 2 sets of non-inferiority hypotheses (1 dose and 2 doses) controlling the family-wise error rate at alpha = 0.025 (1-sided)

Figure 1: Decision Tree-Based Hypothesis Testing

For all comparisons, an NI margin of 2/3 for the GMC ratio will be used. Multiplicity adjustments and more details on the analyses are provided in Section 5.

3. SAMPLE SIZE DETERMINATION

The number of participants chosen is to provide sufficient power for the non-inferiority comparisons.

The following assumptions were made in the sample size determinations:

Log transformed (\log_{10} scale) immune response data are normally distributed

A common standard deviation (SD): SD=0.5 (\log_{10} scale) of the immune response log transformed data

Non-inferiority margin = $\log_{10}(2/3) = -0.176$

Alpha = 0.0125 (1-sided) for 1- and 2-dose NI comparisons

- Alpha = 0.025 (one-sided). Using a Bonferroni correction, Type I error will be split equally over the 1-dose and 2-dose comparisons: 0.0125 (1-sided) for 1- and 2-dose NI comparisons

Power = 90%

Based on the above assumptions, and approximately a 10% dropout, a sample size of 225 participants per active vaccine group (see [Table 2](#)) is needed to detect non-inferiority of testing 1-dose and 2-doses of 9×10^{10} vp, 2.5×10^{10} vp, 7×10^{10} vp, 3.5×10^{10} vp, and 1.25×10^{10} vp Ad26.COV2.S as the test groups versus 1-dose and 2-doses of 5×10^{10} vp Ad26.COV2.S (release titer) as the reference groups, with 90% power (main study sample size assessment).

The originally intended NI population was comprised of participants from the main study who were SARS-CoV-2 seronegative at baseline and non-previously vaccinated. In addition, participants becoming infected with SARS-CoV-2 during the study are excluded from this population from the time of infection.

Participants were screened using a local SARS-CoV-2 serology test to ensure only participants who were seronegative at baseline were enrolled in the main study. However, a preliminary blinded evaluation of central N-serology results in main study participants at Day 29 and Day 71 showed that overall, 27% and 38% of participants, respectively, were N-serology positive at these time points. The higher-than-expected N-serology positive status at Day 29 and Day 71 indicated that participants became infected during the study and/or local serology tests were not sufficiently sensitive, affecting the power of the study.

For the sub-study (initiated to further characterize the innate, pro-inflammatory and other relevant (e.g., prothrombotic) responses to Ad26.COV2.S to better understand a possible risk to TTS events), a target of approximately 240 participants will be enrolled and will receive a 2-dose vaccination regimen at either 9×10^{10} vp, 2.5×10^{10} vp, 5×10^{10} vp, or 1.25×10^{10} vp. As participants in the sub-study share common blood sampling timepoints with the main study, data from both cohorts can be merged for analyses. Due to the higher-than-expected N serology positive results in the main study affecting the power of the study, the non-inferiority assessment will combine participants from the main study and sub-study.

Table 4 below shows how, when combining main and sub study participants (randomized as SARS-CoV-2 seronegative at baseline based on local serology by finger prick testing), the power is affected due to a hypothetical 10%, 20%, 30%, 40%, 50% and 60% loss of evaluable participants (lost due to various reasons, e.g. lost to follow-up, participants with major protocol deviations with impact on immunogenicity, participants who become infected with SARS-CoV-2, participants who received their vaccination outside the allowed window, etc.).

Table 4: Impact of loss of evaluable subjects on NI assessment power

Dose level	Sample size at enrollment per arm (main study + sub study)	Group	% loss of evaluable participants since enrollment					
			10%	20%	30%	40%	50%	60%
9x1010 vp	265(225+40)	1	94%	91%	87%	81%	73%	62%
2.5x1010 vp	265(225+40)	5	94%	91%	87%	81%	73%	62%
7x1010 vp	225 (225+0)	2	90%	86	81%	74%	65%	54%
5x1010 vp	265(225+40)	3	94%	91%	87%	81%	73%	62%
3.5x1010 vp	225 (225+0)	4	90%	86	81%	74%	65%	54%
1.25x1010 vp	265(225+40)	6	94%	91%	87%	81%	73%	62%

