9.2. Sample Size Determination

The number of participants chosen is to provide sufficient power for the non-inferiority comparisons stated in Section 9.1.

The following assumptions were made in the sample size determinations:

- Log transformed (log10 scale) immune response data are normally distributed
- A common standard deviation (SD): SD 0.5 (log10 scale) of the immune response log transformed data
- Non-inferiority margin $\log_{10}(2/3) = -0.176$

- Alpha 0.025 (one-sided). Using a Bonferroni correction, Type I error will be split equally over the 1-dose and 2-dose comparisons: 0.0125 (1-sided) for 1- and 2-dose NI comparisons
- Power 90%

Based on the above assumptions, assuming approximately a 10.2% dropout, a sample size of 225 participants per active vaccine group (see [Table 1](#)) is needed to detect non-inferiority of testing 1-dose and 2-doses of 9×10^{10} vp, 2.5×10^{10} vp, 7×10^{10} vp, 3.5×10^{10} vp, and 1.25×10^{10} vp Ad26.COV2.S as the test groups versus 1-dose and 2-doses of 5×10^{10} vp Ad26.COV2.S (release titer) as the reference groups, with 90% power.

A target of approximately 240 participants (40 seronegative and 20 seropositive participants) per dose regimen in Groups 1, 3, 5, and 6 will be enrolled to further characterize the innate, pro-inflammatory and other relevant (eg, pro-thrombotic) responses to Ad26.COV2.S to better understand a possible risk to TTS events. This target may not be met due to the challenges of enrolling seronegative subjects into the study, so sub-study enrollment may stop at lower numbers.

Participants in the main study and sub-study (participants who are seronegative at enrollment or baseline) may be combined for the analysis.

[Table 7](#) shows how the power will be affected with 10%, 20%, 30%, 40%, 50% and 60% dropout due to various reasons (eg, lost to follow-up, participants with major protocol deviations with impact on immunogenicity, participants who become N-seropositive during the study or with a confirmed SARS-CoV-2 infection, and participants who received their vaccination outside the allowed window).

Table 7: Power Based on % of Drop Out

Regimen	sample size at enrollment per arm	group	% drop out since enrollment					
			10%	20%	30%	40%	50%	60%
9×10^{10} vp (sample size of main study and sub-study)	252 (212+40)	1	92.00%	88.60%	83.70%	76.80%	68.10%	57.20%
2.5×10^{10} vp (sample size of main study and sub-study)	252 (212+40)	5	92.00%	88.60%	83.70%	76.80%	68.10%	57.20%

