4.2. Selection of NI dataset

Decision for selection of population for non-inferiority testing

Participants were screened using a local SARS-CoV-2 serology test to ensure that only participants who were seronegative at baseline were enrolled in the main study (or randomized as seropositive

or seronegative at baseline in the sub study). Prior to Primary Analysis, a preliminary blinded evaluation of central N-serology results in main study participants at Day 29 and Day 71 showed that overall, 27% and 38% of participants, respectively, were N-serology positive at these time points. The higher-than-expected N-serology positive status at Day 29 and Day 71 indicated that participants became infected during the study and/or local serology tests were not sufficiently sensitive, affecting the power of the study.

While data following SARS-CoV-2 infections during the study will be excluded from non-inferiority assessments, data from participants who are seropositive at baseline as assessed by central testing could be included in the non-inferiority assessment if serostatus at baseline is considered as an independent variable (scenario 2).

Based on these considerations, only one of two scenarios will be considered for primary analysis. If there is an overall loss of > 40% evaluable data points in the NI set at Day 29 (defined as number of evaluable participants in the NI set at D29/total number of subjects in Table 4), the population in scenario 2 will be used for primary analysis.

Scenario 1 (base case scenario): non-inferiority will be performed on the NI set including participants from the main study and sub-study.

Scenario 2: Non-inferiority analysis will be performed on the PPI set including participants from the main study and sub-study. In this scenario a model accounting for SARS-CoV-2 serostatus at baseline will be used.

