5.5.3. Analysis Methods

Formal non-inferiority hypothesis testing will be performed on either the NI set (Scenario 1) or on the PPI set (Scenario 2) as described in Section 4.

Descriptive non-inferiority and additional immunogenicity assessments may be performed on other populations and subgroups (e.g., PPI, or on participants in the PPI who are SARS-CoV-2 seropositive at baseline, etc.).

Immunogenicity analyses may also be done on the FAS (participants who became infected during the study will be analyzed as a subgroup and will be shown in the graphs using different colors

and symbols). Samples taken outside of the allowed windows as described in section 5.1.3 (included in the FAS analysis and excluded from the output in the analysis on PPI) will be included and flagged in the listings as results not included in the PPI analyses.

Key immunogenicity subgroup analyses will also be performed by age group, sex, BMI, race, ethnicity, and serostatus at baseline, as defined in Section 5.1.5.

Categorical variables will be summarized with a frequency table showing counts and percentages.

Continuous variables will be summarized using the following statistics, as appropriate: number of observations, geometric mean, arithmetic mean (mean), 95% confidence interval (CI) for the mean, standard deviation (SD), standard error (SE), median, quartiles (Q1 and Q3), minimum and maximum.

Data listings, participant profiles and/or participant narratives may be provided as appropriate.

Binary variables will be summarized using the following statistics: number of observations, percentages, and Exact Clopper-Pearson 95% CIs.

Formal NI testing will be applied to demonstrate NI of 1-dose and 2-doses of 9×10^{10} vp, 7×10^{10} vp, 3.5×10^{10} vp, 2.5×10^{10} vp and 1.25×10^{10} vp Ad26.COV2.S versus 1-dose and 2-doses of 5×10^{10} vp Ad26.COV2.S (release titer), using a NI margin of 2/3 for the GMC ratios.

The following 2 sets of hypotheses (1 dose and 2 doses) will independently be tested sequentially:

Post-dose 1

1a) NI after 1-dose of Ad26.COV2.S 9×10^{10} vp versus 1-dose of Ad26.COV2.S 5×10^{10} vp (release titer)

1b) NI after 1-dose of Ad26.COV2.S 2.5×10^{10} vp versus 1-dose of Ad26.COV2.S 5×10^{10} vp (release titer)

1c) NI after 1-dose of Ad26.COV2.S 7×10^{10} vp versus 1-dose of Ad26.COV2.S 5×10^{10} vp (release titer)

1d) NI after 1-dose of Ad26.COV2.S 3.5×10^{10} vp versus 1-dose of Ad26.COV2.S 5×10^{10} vp (release titer)

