[Figure 1](#) depicts a tree-based schema for testing the non-inferiority hypotheses controlling the family-wise error rate (FWER) at $\alpha = 0.025$ (one-sided). Non-inferiority of immunogenicity will be assessed by first constructing the 2-sided $(1 - \alpha) \%$ confidence interval for the difference in means based on the sampling distribution of two independent normal distributions with variances that are unknown but assumed equal.

Let $X_g = \log_{10} Y_g \sim N(\mu_g, \sigma_g)$, normally distributed with true population mean and standard deviation, μ_g and σ_g respectively and where X_g is the log-transformed (\log_{10} scale) SARS-CoV-2 S-protein specific antibody concentration (ELISA) data for vaccine dose levels, $\mathbf{g} = \mathbf{A}, \mathbf{B}, \mathbf{C}, \mathbf{D}, \mathbf{E}$ in each hypothesis test (so defined to reflect the hypotheses in

[Figure 1](#) in section 1.3),

Where, $A = 9 \times 10^{10}$ vp; $B = 2.5 \times 10^{10}$ vp; $C = 3.5 \times 10^{10}$ vp; $D = 7 \times 10^{10}$ vp; $E = 1.25 \times 10^{10}$ vp

Let $X_r = \log_{10} Y_r \sim N(\mu_r, \sigma_r)$, where X_r is the log-transformed (\log_{10} scale) SARS-CoV-2 S-protein specific antibody concentration (S-ELISA) data for vaccine dose level 5×10^{10} vp (release titer), the reference dose level, r.

It can be shown that the log-transformed (\log_{10} scale) SARS-CoV-2 S-protein specific antibody concentration (S-ELISA) mean differences between the vaccine dose levels g , $(\bar{X}_g - \bar{X}_r)$, is equal to the log-transformed (\log_{10} scale) ratio of the corresponding geometric means, i.e., $\log_{10}(GMC_g/GMC_r)$

Hence, back transforming yields, $GMC_g/GMC_r = 10^{(\bar{X}_g - \bar{X}_r)}$ as the geometric mean ratio estimates.

Next, we can construct the $(1 - \alpha) \%$ confidence interval (2-sided) for the geometric mean ratios, by first constructing the confidence interval on the difference on the means, $(\bar{X}_g - \bar{X}_r)$.

Assuming unknown equal variances for the population vaccine dose levels g and release titer, reference dose level, r , and log-transformed (log₁₀ scale) SARS-CoV-2 S-protein specific antibody concentration (S-ELISA, the $(1 - \alpha)$ % confidence interval (2-sided) estimate for the population vaccine dose level g and reference dose level r mean differences, is given by,

$$(\bar{X}_g - \bar{X}_r) \pm t_{(1-\alpha/2; v_p)} S_p \sqrt{\left(\frac{1}{n_g} + \frac{1}{n_r}\right)}$$

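### SAP Table 4 understates power for the 7 and 3.5×10¹⁰ vp doses by 2.4 to 3.9 points, and the SAP 5.5.3.1 dose key swaps these two doses

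*SAP*

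**What the plan says.** SAP Section 3 states that the non-inferiority assessment pools main-study and sub-study participants. It presents the resulting power with "Table 4 below shows how, when combining main and sub study participants". The table lists 265 (225+40) for the 9, 5, 2.5 and 1.25×10¹⁰ vp arms, so the pooled 5×10¹⁰ reference is 265. It lists 225 (225+0) for the 7 and 3.5×10¹⁰ arms.

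The protocol has its own version, "Table 7: Power Based on % of Drop Out", in Section 9.2. There the same arms are listed at 252 (212+40) and 212.

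SAP 4.2 uses Table 4 a second time. The loss that triggers the change of primary analysis population is "defined as number of evaluable participants in the NI set at D29/total number of subjects in Table 4".

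On the order of tests, SAP 5.5.3 says "The following 2 sets of hypotheses (1 dose and 2 doses) will independently be tested sequentially" and puts 7 at 1c/2c and 3.5 at 1d/2d, as do SAP 2 and Protocol 9.1. The key in SAP 5.5.3.1 assigns letters A to E to the dose levels "in each hypothesis test (so defined to reflect the hypotheses in" Figure 1, with C = 3.5 and D = 7. In SAP 1.1 the pair of two-dose objectives beginning "NI after 2-doses of Ad26.COVID-19 2.5" appears a second time, after the 3.5 pair.

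**The concern.** Table 4 is the SAP's statement of the power of the combined analysis. If the rows for 7 and 3.5 use a 225 reference, they do not describe the comparison that will be made, and they exaggerate how far 7 lags behind 2.5. That lag is the stated reason for testing 2.5 before 7. Table 4 also fixes the denominator of the switch rule, so a disagreement with the protocol about enrollment sizes matters beyond power.

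The key sits in the section that specifies the confirmatory test. In a fixed sequence, position decides which claims are lost when a test fails. With 7 third, a failure of 7 blocks 3.5; with the two swapped, the reverse holds.

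**Working it through.** **Inputs.** From SAP Section 3: "Alpha = 0.0125 (1-sided) for 1- and 2-dose NI comparisons"; "A common standard deviation (SD): SD=0.5" on the log10 scale; margin log10(2/3) = −0.1761. Two assumptions are not in the documents: a true GMC ratio of 1, and the same loss fraction in both arms.

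**Formula.** With n₁ and n₂ evaluable participants, δ = 0.1761 / [0.5·√(1/n₁ + 1/n₂)]. Power is P(T > t₀.₉₈₇₅) for a noncentral t with n₁ + n₂ − 2 degrees of freedom and noncentrality δ. The normal approximation is Φ(δ − 2.2414).

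**Check on the planned size.** n per arm = 2 × 0.5² × (2.2414 + 1.2816)² / 0.1761² ≈ 200.1, so 201. With 10.2% dropout, 201/0.898 ≈ 224, against 225 stated. The inputs are recovered.

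**SAP Table 4 (noncentral t, %).**

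| Loss | 10% | 20% | 30% | 40% | 50% | 60% |
|---|---|---|---|---|---|---|
| 265 v 265 | 94.5 | 91.5 | 87.3 | 81.2 | 73.0 | 62.1 |
| Printed, 265 arms | 94 | 91 | 87 | 81 | 73 | 62 |
| 225 v 225 | 90.2 | 86.2 | 80.8 | 73.8 | 65.0 | 54.2 |
| Printed, 7 and 3.5 | 90 | 86 | 81 | 74 | 65 | 54 |
| 225 v 265 | 92.4 | 88.9 | 84.1 | 77.5 | 68.8 | 57.9 |
| Printed minus 225 v 265 | −2.4 | −2.9 | −3.1 | −3.5 | −3.8 | −3.9 |

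The 265 rows reproduce to about half a point. The 7 and 3.5 rows match 225 v 225 in all six columns and 225 v 265 in none. With a test arm of 225, only reference sizes of about 222 to 229 fit all six printed values. One-sided alpha 0.025 fits no row.

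By hand at 40% loss, using the normal approximation:
- 225 v 265 leaves 135 and 159. δ = 0.1761 / [0.5·√(1/135 + 1/159)] = 3.009, and Φ(0.768) = 77.9%.
- 225 v 225 leaves 135 and 135. δ = 2.893, and Φ(0.652) = 74.3%.

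**Gap between 2.5 and 7 in Table 4.** Printed: 4/5/6/7/8/8 points. With 265 as the reference for both doses: 2.0/2.6/3.2/3.7/4.1/4.1 points.

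**Protocol Table 7.**
- 252 v 252 gives 93.3/90.0/85.4/79.0/70.5/59.6; printed 92.0/88.6/83.7/76.8/68.1/57.2.
- 212 v 252 gives 90.9/87.0/81.8/74.9/66.1/55.3; printed 89.4/85/79.9/72.7/63.7/53.0.

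The printed rows are 1.3 to 2.4 points low. The gap between 2.5 and 7 is about right (printed 2.6 to 4.4, recomputed 2.4 to 4.4). The cause cannot be identified: 240 v 240 with 200 v 240 fits, and so does 252 v 225 with 212 v 225.

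**Switch denominator.** Table 4 sums to 4 × 265 + 2 × 225 = 1,510, and Table 7 to 4 × 252 + 2 × 212 = 1,432. Reading the loss as one minus the stated ratio, the 40% cut is 0.60 × 1,510 = 906 evaluable participants. If 1,432 were in fact enrolled (an assumption; the documents do not say), 906/1,432 = 63.3%, so the cut falls at 36.7% loss.

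**Order of tests.**

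| Position | Protocol 9.1, SAP 2, SAP 5.5.3 | Key in SAP 5.5.3.1 |
|---|---|---|
| a / A | 9 | 9 |
| b / B | 2.5 | 2.5 |
| c / C | 7 | 3.5 |
| d / D | 3.5 | 7 |
| e / E | 1.25 | 1.25 |

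**The case against.** The arithmetic is not in dispute; the weight is. The power error is conservative, and the planned size of 225 does not depend on it. No row crosses 80% at a tabulated loss (81 becomes 84 at 30%; 74 becomes 77.5 at 40%). The change of order does not rest on Table 4: Protocol 9.1 cites Table 7, whose gap is about right. Table 4 even prints a power for the reference arm, which suggests an equal-arm lookup by arm size that a footnote could explain. The key letters only index a confidence-interval formula that is the same for every dose, and all numbered lists agree. The switch denominator is determinate as written, and 36.7% needs an unstated enrollment figure.

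Most of this stands, and it limits the consequences. 7 still has less power than 2.5, the key is most likely a labelling slip, and the repeated 2.5 pair has no inferential effect. Figure 1 is not visible in the text reviewed, so its order cannot be checked. The lookup reading explains how the figures may have arisen but does not make them right. The SAP offers them as the power of the combined analysis, and for two of the five test doses they are not. The key says it mirrors the hypotheses, and it contradicts the numbered ones.

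**Conclusion.** The point holds. SAP Table 4 understates power for the 7 and 3.5×10¹⁰ vp doses by 2.4 to 3.9 points and roughly doubles the apparent handicap of 7 relative to 2.5. Protocol Table 7 is 1.3 to 2.4 points low for its printed sizes, and the two tables give different enrollment sizes for the same arms. The dose key in SAP 5.5.3.1 conflicts with every numbered hypothesis list. The power figures rest on a true ratio of 1 and equal loss in both arms; the first is supported by its reproducing the planned size and the printed Table 4 rows. These are errors in confirmatory text that should be corrected. They do not undermine the design or the test order.

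**What to change.** - Restate the Table 4 rows for 7 and 3.5×10¹⁰ vp against the 265 reference: 92/89/84/77/69/58%.
- Recompute Protocol Table 7 for its listed sizes, or state the sizes that were used.
- Reconcile 265/225 with 252/212, and say which total is the denominator in SAP 4.2.
- Set the SAP 5.5.3.1 key to C = 7 and D = 3.5, to match Protocol 9.1.
- Delete the repeated 2.5 pair in SAP 1.1.
- Check that the decision figure and the list in Protocol 2.1 show the same single order. Protocol 2.1 prints no conditional step between 2.5 and 7 in its one-dose list.

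This should be done before unblinding. SAP version 3 is dated 04/07/2023, so that point may have passed; a dated erratum would then serve. The cost is wording and table entries only, with no new data and no change to sample size, margin, alpha, test order or analysis method.
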